5.1.3 Justification of selection criteria

The selection criteria were carefully selected to exclude subjects from the study who may potentially be exposed to specific risks after administering the study drug as well as subjects with conditions that may have an impact on the aims of this study.

5.2 Withdrawal of subjects from study

5.2.1 Withdrawal

Subjects *must* be withdrawn from the study for the following reasons:

- At their own request or at the request of their legally acceptable representative
At any time during the study and without giving reasons, a subject may decline to participate further. The subject will not suffer any disadvantage as a result.
- If serum transaminases are greater than 3 times the upper limit of normal
- If serum CPK elevations are greater than 5 times the upper limit of normal.
- If, in the investigator's opinion, continuation of the study would be harmful to the subject's well-being
- Occurrence of AEs or intercurrent diseases which the investigator judges unacceptable for continuation of participation in the study
- Occurrence of adverse drug reactions, which in the investigator's opinion have a negative impact on the subject's individual risk-benefit ratio.
- Non-compliance with the conditions for the trial or instructions by the investigator
- Although not preferred, subjects may interrupt their intake of study medication for reasonable circumstances/reasons at any time (eg, hospitalization in a remote hospital without study medication access, safety reasons, and side effects). If an interruption lasts longer than 14 consecutive days, the subject must be withdrawn. In case treatment requires interruption for > 3 days and ≤ 14 days, it is at the discretion of the investigator if the study medication can be restarted.
- In case of pregnancy or breast feeding.
- In case the subject does not tolerate the drug.

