4.1.2 Study Treatment phase (Week 0 to Week 16)

At the baseline (week 0) visit, subjects who have met all of the inclusion and none of the exclusion criteria will be randomized using a 1:1 randomization scheme that will be regulated centrally through the UPMC IDS. Each patient enrolling in the study will be assigned an ID. At week 0 patients will undergo assessment of Raynaud activity/severity and noninvasive vascular imaging.

Patients will have a visit at week 8 to assess safety, tolerability and adverse effects of the study drug. Raynaud activity/severity and DU will be assessed.

Patients will have a final end of study visit at week 16 to assess safety, tolerability and adverse effects of the study drug. They will also undergo assessment of Raynaud activity/severity and noninvasive vascular imaging.

Dose Interruptions

If treatment is interrupted for any reason the following rules should be applied:

- ≤ 14 consecutive days without treatment it is at the discretion of the investigator if the study medication can be restarted
- >14 consecutive days without treatment: withdraw the subject from study medication.

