5.2.2 Replacement

There will be no replacement of randomized subjects who withdraw from the study.

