6.6 Drug logistics and accountability

A drug dispensing log will be completed for each subject. Subjects will receive all study medication dispensed at the baseline visit. At weeks 8 and 16, subjects will be instructed to bring all study drug packaging, including unused study drug and empty packaging, to the investigative site at each study visit. Tablets will be counted for a compliance check and drug accountability. At week 16, unused study drug will be returned to the IDS for destruction.

If a dose of study drug is missed, the subject should take a dose immediately if on the same day. Otherwise, they can resume normal once daily dosing the following day. The dose should not be doubled to make up for a missed dose within the same day.

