8.1 General considerations

An intention to treat analysis will be performed including all who receive one dose of drug. Initial analysis will describe the baseline population, sociodemographic and clinical characteristics, and compare by treatment group. Means of continuous measures will be conducted using a t-test or Wilcoxon test and discrete measures compared with a chi-square test. The goal of all trial analyses is to provide effect size estimates for design of a later phase 3 clinical trial of statin therapy in early diffuse SSc, if deemed appropriate. If not mentioned otherwise, all statistical tests will be performed with a type I two-sided error rate of $\alpha=5\%$.

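### Non-compliance is a mandatory reason to leave the study, not only to stop study drug, so the intention-to-treat analysis can lack a week 16 RHI by rule

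*Combined protocol and SAP*

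**What the plan says.** Section 5.2.1 opens its list by saying that subjects must "be withdrawn from the study for the following reasons". One entry is "Non-compliance with the conditions for the trial or instructions by the investigator". No adherence threshold is given. The same list says "If an interruption lasts longer than 14 consecutive days, the subject must be withdrawn", whereas section 4.1.2 says for the same event ">14 consecutive days without treatment: withdraw the subject from study medication". The protocol therefore knows both concepts, leaving the study and leaving the drug, but does not keep them apart.

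Section 5.2.2 adds "There will be no replacement of randomized subjects who withdraw from the study". Section 6.6 has patients bring their packaging at weeks 8 and 16, and "Tablets will be counted for a compliance check and drug accountability".

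On analysis, 8.1 states "An intention to treat analysis will be performed including all who receive one dose of drug" and also "The goal of all trial analyses is to provide effect size estimates for design of a later phase 3 clinical trial". Section 8.2.2 defines the primary outcome as the change in RHI from baseline to week 16, compared between arms by t-test. Nothing in section 8 says what happens when the week 16 RHI is missing.

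Section 7.1.2.5 covers early discontinuation of study drug. Patients with 8 weeks or more of therapy have the Week 16 procedures, which include EndoPAT. Patients who stop earlier have the Week 8 procedures, which do not.

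**The concern.** Most entries in the 5.2.1 list reflect consent or safety. Non-compliance alone reflects neither: the patient may still agree to take part and be able to attend at week 16. Ending participation for that reason makes the primary outcome missing, or measured at another time, because of the protocol rather than the patient.

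Adherence is observed after randomisation and may depend on the assigned treatment. Section 7.5.1.6 expects myalgia or arthralgia in more than 10% of patients on atorvastatin, and lack of benefit could play the same part on placebo. If patients selected in this way drop out of the t-test, the comparison is no longer between the groups as randomised. With 15 per arm, a few such patients matter, and the estimate is meant to inform the design of a phase 3 trial.

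**Working it through.** **1. What a patient withdrawn for non-compliance contributes**

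- Stopped before 8 weeks: Week 8 procedures (7.1.2.3), no vascular imaging. There is no RHI after baseline, so a t-test of change can only omit the patient.
- Stopped at 8 weeks or later, before week 16: EndoPAT at discontinuation. An RHI exists, but at an earlier time and after shorter treatment than 8.2.2 specifies. No text says whether it is used.
- Found at the week 16 tablet count: the final visit, with EndoPAT, is already due. Nothing need be lost.

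The week 8 visit has a window of 7 days either side, so it can fall on day 56 − 7 = 49. A patient withdrawn after a tablet count at such a visit has had less than 8 weeks of therapy and comes under the first case.

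Section 7.1.2.5 is worded for stopping study drug. Sections 4.1 and 4.1.3 give a termination visit to patients who withdraw as well, but do not say that it includes EndoPAT.

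**2. The plan's own precision figure**

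Section 8.4 gives ±0.374 with 15 per arm and states no SD. The usual formula is half-width = t(0.975, n1 + n2 − 2) × SD × √(1/n1 + 1/n2). Solving for the SD gives 0.374 / (2.0484 × √(2/15)) = 0.500. With the normal quantile it would be 0.523. The round 0.50 is the likelier source. It is implied, not stated, and the figure takes all 30 patients as evaluable.

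**3. Precision if patients are lost** (SD 0.50; numbers lost are assumed; no early-termination RHI used)

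| Evaluable per arm | Calculation | Half-width |
|---|---|---|
| 15 | 2.0484 × 0.50 × √(2/15) | 0.374 |
| 14 | 2.0555 × 0.50 × √(2/14) | 0.388 |
| 13 | 2.0639 × 0.50 × √(2/13) | 0.405 |
| 12 | 2.0739 × 0.50 × √(2/12) | 0.423 |

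**4. Dilution illustration**

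Suppose a fraction f of the active arm adheres poorly and keeps a share r of the drug effect, and that poor adherers are otherwise like the rest. The effect over all randomised patients is then (1 − f) + f × r times the effect in adherers. If the poor adherers are omitted, the estimate is too large by 1 / [(1 − f) + f × r] − 1.

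| Omitted, of 15 active | r = 0 | r = 0.5 |
|---|---|---|
| 1 | 15/14 − 1 = 7% | 30/29 − 1 = 3% |
| 2 | 15/13 − 1 = 15% | 30/28 − 1 = 7% |
| 3 | 15/12 − 1 = 25% | 30/27 − 1 = 11% |

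**5. Why the direction is open**

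Suppose the drug does nothing, and in each arm 3 of 15 patients adhere poorly and have a mean RHI change lower by g than the others (taken as 0). After k of the three are removed, the arm mean is −(3 − k) × g / (15 − k). Removing 3 on active and 1 on placebo gives a spurious difference of 0 + 2g/14 = g/7, which is 0.036 for g = 0.25 and 0.071 for g = 0.50. Swapping the arms reverses the sign. Removing 2 from each arm gives zero.

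**The case against.** The strongest reply is that 7.1.2.5 already protects the endpoint. The first scheduled tablet count is at week 8, so many poor adherers found that way will have had about 8 weeks of therapy and will have EndoPAT when they stop. This stands in part. A reader might infer from 5.2.1 that every patient withdrawn for non-compliance is lost without a follow-up RHI, and the documents do not support that. The protection does not reach those who stop before 8 weeks, and for the others no text lets the off-schedule value into the analysis.

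A reader might also infer that 5.2.1 contradicts 8.1 or amounts to a per-protocol rule. It does not. Section 8.1 defines who is analysed and 5.2.1 governs participation, so a withdrawn patient who took one dose stays in the analysis set. Harm arises only if that patient's outcome is missing and the analysis uses complete cases.

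Third, the non-compliance entry is general. It does not name tablet adherence, and 6.6 does not link the count to withdrawal. Section 6.6 also tells patients how to resume after a missed dose, so someone with scattered missed doses is not clearly covered. That is fair: with no threshold, how often the entry would be applied is unknown.

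Finally, deleting the entry would go too far. It can also reach trial conditions such as prohibited medication and contraception, and losses due to side effects fall mainly under other entries in the list. This objection stands and shapes the remedy.

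**Conclusion.** The point holds in a limited form. As written, the plan can make the primary outcome missing, or move it off schedule, in patients who could have supplied it at week 16, and it says nothing about how the analysis then proceeds. Sections 4.1.2 and 5.2.1 also disagree on whether a long interruption ends treatment or participation, and they must be reconciled.

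The size and direction of any bias cannot be derived, because the documents give no non-compliance rate, no expected effect and no SD. The range of 3% to 25% assumes complete-case analysis, 1 to 3 losses in the active arm only, and non-adherers who keep between none and half of the benefit. The range of 0.388 to 0.423 assumes 1 to 3 losses per arm and an SD of 0.50. Both shrink if early-termination readings are used. It would be wrong to quote any one of these values, such as 15%, as the expected bias.

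This should be changed, because the remedy is cheap and the stated purpose of the trial is effect size estimation.

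**What to change.** - In 5.2.1 and 7.1.2.5, state that non-compliance alone does not end study follow-up. Whatever is decided clinically about study drug, patients who still consent keep the scheduled week 16 visit with EndoPAT and are analysed as randomised.
- Reconcile 4.1.2 with 5.2.1 on interruptions over 14 days, saying in each place whether study drug or study participation is meant.
- Record non-compliance as a protocol deviation, which 10.1 already requires to be documented, together with the tablet count. Report adherence by arm.
- In 8.2.2, state how an RHI taken at early termination and a missing RHI enter the intention-to-treat analysis.

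The cost is a few sentences and visits that are already scheduled. A small downside is that the estimate will include poor adherers and may be slightly smaller, as intention to treat intends. No change to any clinical stopping rule is proposed.

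### Sections 4.1.2 and 5.2.1 contradict each other on dose interruptions, and no section keeps a participant who stops study drug in follow-up to the week-16 RHI

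*Combined protocol and SAP*

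**What the plan says.** All references are to the combined protocol and SAP.

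- **Section 4.1.2, Dose Interruptions.** For shorter gaps: "≤ 14 consecutive days without treatment it is at the discretion of the investigator if the study medication can be restarted". For longer ones: ">14 consecutive days without treatment: withdraw the subject from study medication".
- **Section 5.2.1, Withdrawal.** The list opens by saying that subjects must "be withdrawn from the study for the following reasons". One item reads: "In case treatment requires interruption for > 3 days and ≤ 14 days, it is at the discretion of the investigator". The same item says: "If an interruption lasts longer than 14 consecutive days, the subject must be withdrawn".
- **Section 6.6**, on a missed dose not taken the same day: "Otherwise, they can resume normal once daily dosing the following day". It mentions no investigator decision.
- **Sections 4.1 and 4.1.3** give a termination visit and a 30-day safety visit both to those who stop drug and to those who withdraw.
- **Section 7.1.2.5** sets the early-stop assessments by time on therapy: Week 16 procedures from 8 weeks onward, Week 8 procedures before that.
- **Section 8.1**: "An intention to treat analysis will be performed including all who receive one dose of drug".
- **Section 8.2.2** makes the primary outcome the change in EndoPAT RHI from baseline to week 16. **Section 5.2.2** rules out replacing those who withdraw.

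**The concern.** Stopping study drug and leaving the study are different events, and section 4.1 itself names them separately. An intention-to-treat comparison of week-16 change needs the week-16 measurement from people who have stopped drug as well as from those still taking it. If the protocol is unclear on what a participant is withdrawn from, and silent on follow-up after stopping, site staff have no instruction to obtain that measurement.

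The participants concerned may not be a random subset. Section 5.2.1 gives hospital stays, safety reasons and side effects as examples of why drug is interrupted. Its mandatory-withdrawal list also includes raised transaminases, raised CPK and intolerance. Section 7.5.1.6 describes liver and muscle effects as known risks of atorvastatin. Loss of the outcome could therefore differ between arms. With 30 participants and a stated aim of supplying effect-size estimates for a phase 3 trial, a few missing values carry weight.

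**Working it through.** **1. The interruption rules side by side**

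| Length of gap | Section 4.1.2 | Section 5.2.1 | Section 6.6 |
|---|---|---|---|
| 1–3 days | investigator's discretion | no restart rule stated | missed dose: resume next day |
| More than 3, up to 14 days | investigator's discretion | investigator's discretion | – |
| More than 14 days | withdrawn from study medication | listed for withdrawal from the study | – |

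The sections disagree in the first and third rows and agree in the second.

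**2. What happens to the primary outcome**

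EndoPAT appears in the section 7.1.1 schedule at baseline and week 16 only. The Week 8 list in section 7.1.2.3 has no vascular imaging; the Week 16 list in section 7.1.2.4 does. Applying section 7.1.2.5:

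- *Drug stopped before 8 weeks:* Week 8 procedures, so no post-baseline EndoPAT is specified and the RHI change does not exist.
- *Drug stopped at 8 weeks or later:* Week 16 procedures, including EndoPAT, triggered by discontinuation. The measurement need not fall at week 16.

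Both results are the same whether the participant is taken to have left medication or the study, because sections 4.1 and 4.1.3 assign the same visits to both. No section sends either participant on to the scheduled week-16 EndoPAT session.

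**3. Against the analysis plan**

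Section 8.1 includes both participants. Section 8.2.2 compares change to week 16 and gives no rule for a missing RHI or for one measured early.

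**4. Scale only**

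The plan's single precision figure is ±0.374 with 15 per group (section 8.4). The formula for the half-width is

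h = t(0.975, n1 + n2 − 2) × SD × √(1/n1 + 1/n2).

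No SD is given. Solving h = 0.374 for 15 + 15 gives SD = 0.374 / (2.048 × 0.3651) = 0.500. With a normal quantile it would be 0.374 / (1.960 × 0.3651) = 0.523. SD 0.50 is therefore an assumption, back-solved from the plan's own figure. It returns that figure: 2.048 × 0.50 × 0.3651 = 0.374.

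A loss of 10–20% of RHI values is also an assumption:

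| Evaluable | Calculation at SD 0.50 | h | h at SD 0.40 to 0.60 |
|---|---|---|---|
| 30 (15 + 15) | 2.048 × 0.50 × √(2/15) | 0.374 | 0.299 to 0.449 |
| 27 (14 + 13) | 2.060 × 0.50 × √(1/14 + 1/13) | 0.397 | 0.317 to 0.476 |
| 24 (12 + 12) | 2.074 × 0.50 × √(2/12) | 0.423 | 0.339 to 0.508 |

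Relative widening at SD 0.50: 0.397/0.374 = 1.06 and 0.423/0.374 = 1.13, that is, 6% to 13%.

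**The case against.** A reader might infer that the choice between leaving medication and leaving the study decides whether the week-16 RHI is collected. The documents do not support that. Sections 4.1 and 4.1.3 treat the two groups alike, and section 7.1.2.5 makes EndoPAT depend on whether 8 weeks of therapy were completed. The gap in outcome collection exists under either wording, so reconciling sections 4.1.2 and 5.2.1 alone would not close it.

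Four further objections are fair:

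- The day-range conflict touches only gaps of 1–3 days and has no shown effect on any analysis. This stands; it is a contradiction in the text and no more.
- Section 8.1 defines who is analysed, and missing data do not change that definition. This stands too. The difficulty is that included participants have no planned outcome, not that the population is contradicted.
- Bias is not certain. One listed reason, a stay in a remote hospital without access to study drug, need not relate to arm or outcome.
- The half-widths rest on an assumed SD and loss rate, and they treat every affected participant as having no RHI. Those who stop from 8 weeks onward do have an RHI planned. The figures therefore show the cost of lost values in general and do not measure this conflict.

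None of these removes the two textual contradictions, or the absence of a planned week-16 RHI for participants who stop drug early.

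**Conclusion.** The concern holds in two parts.

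First, sections 4.1.2 and 5.2.1 contradict each other on the range of days left to the investigator and on what a participant off drug for more than 14 days is withdrawn from. This is wrong as written.

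Second, the protocol does not plan a week-16 RHI for participants who stop drug early: none after baseline if they stop before 8 weeks, and one tied to the stop if later. Yet they belong to the analysis set for change to week 16. Changing this is a cheap improvement.

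The size is unknown. The documents give no interruption rate and no SD. The widening of 6% to 13% is for scale only and depends on SD 0.50 and a 10–20% loss. Neither the direction nor the size of any bias can be derived from the documents; the listed reasons for stopping make a difference between arms possible, not established.

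**What to change.** 1. Reconcile sections 4.1.2, 5.2.1 and 7.1.2.5 on the range of days, and on whether the participant leaves study medication or the study. Align the missed-dose text in section 6.6 with the result. This review prefers no interruption or stopping rule; that choice is the sponsor's.
2. Separately, and for outcome collection only, state that stopping study drug does not by itself end follow-up. State also that EndoPAT RHI is sought at the scheduled week 16 for every dosed participant who still consents and for whom the investigator sees no safety objection to the procedure.
3. State in section 8.2.2 how an RHI measured at early termination, or a missing one, enters the intention-to-treat analysis.

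The cost is mainly wording, since the week-16 visit is already in the schedule. The downside is that a few off-drug participants may need a vascular session in addition to the termination and 30-day visits.

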5.2.2 Replacement

There will be no replacement of randomized subjects who withdraw from the study.

5.3 Subject identification

After a subject signs the informed consent form, a subject identification number will be created. This will be a unique code composed of study name and subject number

First 5 letters = TAMER (to identify this as this trial)

Last 4 digits = Unique subject number

6. Treatment

6.1 Treatments to be administered

Test Drug: Atorvastatin

Dosage: 40 mg

Route of administration: oral

Time and frequency of administration: once daily

6.2 Identity of study treatment

Atorvastatin

Atorvastatin will be supplied at 40 mg as film-coated, immediate-release tablets. All study drug and placebo tablets will be provided through the UPMC Investigational Drug Service, who will also be handling patient randomization.

A complete record of batch numbers and expiry dates of all study treatment, as well as the labels, will be maintained in the study file.

Matching placebo

Matching placebo tablets will appear identical to active atorvastatin tablets but will not contain active study drug.

6.3 Treatment assignment

This is a randomized, double-blind, placebo-controlled, parallel-group, single-center study. Subjects who complete all screening procedures and meet all the eligibility criteria are to be randomized in a 1:1 ratio by the UPMC IDS.

6.4 Dosage and administration

6.4.1 Selection of doses in the study

Atorvastatin has been safe and well tolerated in previous clinical studies in the general population, cardiovascular disease populations and systemic sclerosis patients at doses of 40 mg once daily. 40 mg once daily atorvastatin has been shown to improve brachial FMD in patients with cardiovascular disease as well as SSc¹³.

6.5 Blinding

The study will be conducted in double-blind fashion. Active atorvastatin and placebo tablet formulations will be identical in appearance (size, shape, color) and smell. The packaging and labeling will be designed to maintain blinded conditions for the investigator and the study team. The study data will remain blinded until database lock.

Emergency unblinding by the investigator

In case of emergency, the investigator is permitted to unblind individual cases. However, this will be restricted to cases of emergency where the unblinding result is of importance for the acute treatment strategy. The occurrence of an SAE should not routinely precipitate the immediate unblinding of the label. Date, time, and reason for unblinding will be captured. Unblinding will be coordinated through the Investigational Drug Service

